#### Randomisation

Approximately 20 participants will be recruited to the study, with 10 participants assigned to each of the two possible treatment groups. Randomization will be at the patient level and executed through the Bristol Dental Clinical Trials Unit, according to a predetermined randomization schedule.

A unique screening number will identify each subject screened for study participation. Screening numbers will be assigned in ascending numerical order as each subject signs their consent form. Subjects who meet all inclusion and exclusion criteria will be randomised according to the randomisation schedule. Randomisation numbers will be assigned in ascending numerical order as each subject is determined to be fully eligible. The randomisation schedule will be generated via a computer-generated system (using SAS version 9.4).

#### **Statistical Methods**

#### Populations for Analysis

The intent to treat (ITT) population will be defined as all participants randomized to study intervention. Patient data will be analysed according the treatment randomized.

#### Sample Size

This is a pilot study, therefore the sample size of 20 subjects will be for the purposes of estimation rather than hypothesis testing. Hence, a sample size of 10 per group (20 in total) will ensure that the 95% CI for the mean difference in the change from baseline (at week 4) plaque scores lie to within about 0.16 units of any observed difference. For example, if the observed difference was in fact 0.69, the true (population) difference would lie somewhere between 0.607 and 0.772 with 95% confidence (a measure of uncertainty).

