#### Study Design

The study will be a parallel, randomised (1:1 ratio) 2 treatment, single centre study. The study sites will be the University of Bristol Dental School and Hospital including the South Bristol Community Hospital outreach centre, and the general dental practice Redland Park Dental Surgery. The study will be conducted by the Clinical Trials Unit team members who are part of Bristol Dental School.

At Visit 1, following provision of informed consent and confirmation of eligibility to take part in the study, participants will be provided with a questionnaire to complete regarding gum (gingival) health and then shown standard pictures of teeth and gingivae. They will be asked to indicate whether they think the pictures demonstrate oral health or oral disease and which they think represents their current oral health.

The participants will undergo an oral hard and soft tissue examination.

An intra-oral diagnostic camera will then be used by the clinician to take an intra-oral scan including images and a video of the patient's mouth. The images and video captured will be downloaded and a pictorial report prepared of their oral health. The camera software has the ability to detect plaque on the teeth and this will also be used to assess the levels of plaque present on the participant's teeth.

The study dentist will carry out a gum health examination (Modified Gingival Index, MGI) for the participant and will then measure the amount of plaque present using a traditional technique involving placing dye (food colouring) onto the surface of the teeth which highlights plaque (O'Leary et al 1972).

Participants will be randomised by study staff to one of 2 treatment groups (Control group - standard verbal oral health instructions (verbal OHI) or Test group – pictorial report + verbal oral health instructions (picture + verbal OHI) using a predetermined randomisation schedule.

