#### Study dental assessments

The intra-oral camera will record images of the teeth and gums of the patient which will be downloaded to form a pictorial report tailored to the patient. The intra-oral camera also detects and measures plaque levels present on the surface of teeth. This function will be used to assess the plaque levels present on the upper 3-3) prior to any dye being placed on the participants teeth.

The baseline and 4-week plaque and gingival health assessments will be performed by a single dental clinician. Teeth in the upper 3-3 area will be scanned using the intra-oral camera. The teeth for gingival health and plaque assessment within the study will be 2 suitable teeth within the upper 3-3 region as determined by the study clinician. The same 2 teeth will be assessed by the clinician at Visit 1 and Visit 2 for plaque and gingival health.

Plaque scores will be recorded at Visit 1 and 2 following the method established by O'Leary et al (1972). Plaque will be scored using a 2-point code (buccal and lingual/palatal) where NO (0) = no plaque and YES (1) = presence of plaque.

Gingival health will be assessed using the Modified Gingival Index (MGI) (Lobene, 1986) and the gingival bleeding index (BOP) as described by Ainamo & Bay (1975). The MGI index is a non-invasive visual evaluation of gingival health. Each site (2 per tooth) will be classified as healthy or exhibiting gingivitis. If the site exhibits gingivitis the MGI index will be used to assess the degree of gingival inflammation at 2 sites (buccal and lingual/palatal) of each suitable scorable teeth and scored on a 5-point scale. Gum health will also be assessed by recording bleeding on probing. A periodontal probe with a 0.5 mm diameter tip is inserted into the gingival crevice and swept from distal to mesial, around the tooth at an angle of approximately 60° while in contact with the sulcular epithelium. For each tooth assessed, a binary recording of either YES (bleeding observed) or NO (no bleeding observed) for bleeding will be made at 4 sites per tooth. The proportion of bleeding sites compared to all examined sites will provide the percentage of bleeding per participant.

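### The sample-size precision statement and its worked example disagree by a factor of about two, and no standard deviation is given to show which is right

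*Protocol*

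**What the plan says.** The protocol's Sample Size section calls the trial a pilot and states that "the sample size of 20 subjects will be for the purposes of estimation rather than hypothesis testing". It then claims that 10 per group "will ensure that the 95% CI for the mean difference" in change from baseline at week 4 has a given precision: the interval for "plaque scores lie to within about 0.16 units of any observed difference". The illustration follows at once: "if the observed difference was in fact 0.69, the true (population) difference would lie somewhere between 0.607 and 0.772 with 95% confidence". The section gives no SD, formula or source.

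The endpoint is described elsewhere. Under Study dental assessments, two teeth in the upper anterior region are assessed, and "Plaque will be scored using a 2-point code (buccal and lingual/palatal) where NO (0) = no plaque and YES (1) = presence of plaque". Statistical Analyses compares the groups on change in mean plaque level. Study Design describes the trial as "parallel, randomised (1:1 ratio) 2 treatment".

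**The concern.** A statement that an interval lies within 0.16 of the estimate describes a half-width. The example printed beside it has a half-width of about half that size. A reader cannot tell which precision the trial was planned to achieve.

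This matters because precision is the only reason given for recruiting 20 participants; there is no power calculation behind it. The claim is also worded as a guarantee, although the width obtained depends on the SD observed, which sample size alone does not fix. A funder, ethics committee or planner of a later trial who relied on the example would expect a much tighter estimate than this endpoint is likely to give.

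**Working it through.** **Inputs from the protocol.** 10 per group, 1:1, two parallel groups; two-sided 95% interval for the difference in mean change; stated precision 0.16; example 0.69 (0.607 to 0.772); plaque scored 0/1 at 2 surfaces on each of 2 teeth. SD of change: not stated.

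**Step 1: the example against the statement.**
- 0.69 − 0.607 = 0.083 and 0.772 − 0.69 = 0.082, so the half-width is 0.0825.
- 0.772 − 0.607 = 0.165, the full width.
- A half-width of 0.16 would give 0.69 ± 0.16 = 0.53 to 0.85.
- 0.16 / 0.0825 = 1.94.

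**Step 2: the SD that each figure implies.** Half-width = t(0.975, 18) × SD × √(2/10) = 2.101 × 0.4472 × SD = 0.940 × SD.
- 0.0825 / 0.940 gives SD 0.088.
- 0.16 / 0.940 gives SD 0.170.
- With z = 1.960 instead of t, the SDs are 0.094 and 0.183. The choice of quantile does not close the gap.
- At SD 0.170, a half-width of 0.0825 would need about 34 per group rather than 10.

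**Step 3: two explanations that fit.**
- 0.16 may be the full width (0.165) described as a distance from the estimate.
- 0.0825 may be one standard error: 1.96 × 0.0825 = 0.162. Then 0.16 is a proper half-width, and the example is plus or minus one standard error, roughly a 68% interval, labelled as 95%.

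**Step 4: both figures against the endpoint.** Assume that a participant's score is the mean of the four 0/1 sites. It then moves in steps of 0.25.

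*For 0.0825 (SD 0.088).* Suppose everyone in an arm has the same change except a share p who differ by one site. Then 0.25 × √(p(1−p)) = 0.088 gives p = 0.144, so about 86% must change identically. If the exceptions split evenly in both directions, the share is about 88%.

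*Under assumed site prevalences.* Variance of the score at a visit = prev(1−prev)/4 × (1 + 3 × ICC). Variance of change = V1 + V2 − 2 × r × √(V1 × V2), where r is the correlation between visits.

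| Assumed prevalence, r = 0.5 | ICC | SD of change | Half-width |
|---|---|---|---|
| 0.6 to 0.4 | 0 | 0.245 | 0.23 |
| 0.6 to 0.4 | 0.3 | 0.34 | 0.32 |
| 0.9 to 0.8 | 0 | 0.18 | 0.17 |
| 0.9 to 0.8 | 0.3 | 0.25 | 0.23 |

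Across 81 assumed combinations (prevalence 0.3 to 1.0, ICC 0 to 0.4, visit correlation 0 to 0.7), the smallest half-width was 0.101, so 0.0825 was never reached. A half-width of 0.16 or less occurred in 9. Eight of these were near ceiling (0.95 to 0.9, or 1.0 to 0.9). The ninth was 0.9 to 0.7 with visit correlation 0.7 and no clustering of sites.

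**Step 5: half-width by assumed SD, 10 per group.** SD 0.20: 0.19. SD 0.25: 0.23. SD 0.30: 0.28. SD 0.35: 0.33. SD 0.40: 0.38.

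**The case against.** The strongest reply is that little depends on this paragraph. The trial is a pilot, no hypothesis decision or stopping rule uses the figure, and the reported interval will come from the observed data. That stands, and it limits how serious the point is. It does not remove the contradiction, which lies in two adjacent, complete sentences and is not repaired elsewhere in the protocol.

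Four stronger readings are tempting, and the document does not support them.

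- *That 0.16 is certainly a mislabelled full width.* The one-standard-error explanation fits as well, and without an SD neither can be ruled out.
- *That the endpoint cannot deliver ±0.16.* This depends on an SD that the protocol does not give. A prevalence falling from 0.6 to 0.4 puts the site variance at 0.24, close to its maximum of 0.25. Eligibility requires some gingival inflammation on an assessed tooth and the clinician chooses the teeth, so high baseline plaque is also plausible. At 0.9 to 0.8 with independent sites the half-width is 0.17.
- *That 0.69 shows the figures came from another scale.* It would be a large difference on a 0 to 1 score when controls also receive verbal instruction. But it is offered only as an illustration, and its size has no bearing on the half-width.
- *That 20 participants is the wrong number.* Nothing here shows that for a pilot aimed at estimation.

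It is also fair to say that the four-site mean is inferred: the protocol gives 0/1 scoring and mean plaque levels but does not spell out the aggregation. On a 0 to 4 sum, the half-widths would be four times larger.

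**Conclusion.** The precision statement is wrong as written. The stated distance of 0.16 and the example's half-width of 0.0825 differ by a factor of 1.94, and this follows from the protocol's own numbers with no outside assumption. Which of the two is in error cannot be determined from the document.

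The guarantee is also unsupported, since no SD is stated. On a four-site mean score, 0.0825 is implausible because about 86 to 88% of an arm would need the identical change. The figure of 0.16 is optimistic but not excluded: it can be reached near floor or ceiling, or with high correlation between visits. These plausibility judgements assume the four-site mean, 10 complete participants per group, a common SD and an unadjusted comparison, together with the prevalences and correlations shown.

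The point should be corrected, but it does not threaten the trial: the sample size stands and the reported interval is unaffected.

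**What to change.** Keep 20 participants and rewrite the Sample Size paragraph.

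1. State the assumed SD of change in plaque score and its source, on the scale to be analysed, and say how the sites are combined into a participant's score.
2. Recompute both the precision and the example from t(18) × SD × √(2/10) so that they agree. Do not presume that either present figure is the correct one.
3. Describe the result as an expected half-width rather than something the sample size guarantees.
4. Show a range, for instance ±0.19 to ±0.38 for assumed SDs of 0.20 to 0.40 on a 0 to 1 mean score.

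The cost is protocol wording only. No participants are added and the analysis does not change. The stated precision will probably look less favourable.

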#### **Statistical Analyses**

Descriptive statistics (number of subjects, mean, standard deviation, median, minimum and maximum for continuous variables, and frequency and percentage for categorical variables) will be provided for demographic and baseline data.

A mixed effects model with random effects for participants and fixed effect for treatment. The 95% CI along with the mean difference (of change from baseline) in mean plaque levels at 4 weeks for each group will be reported. Adjustment for covariates (e.g. gender, age) will be included in the model.

The primary outcome will also be summarized (using summary statistics) by intervention group, and where appropriate assessment points. Where appropriate and data permitting covariates (e.g. age, gender) will be included in the model. For each secondary outcome, similar analyses will be performed as the primary outcome using a generalized linear model with an appropriate link function depending on the nature of the outcome. Appropriate 95% confidence intervals and p-values will be generated.

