#### Outcomes

#### **Primary Objectives**

• To evaluate patient gingival health and plaque levels prior and following the provision of a pictorial report and tailored OHI over a 4-week.

Gingival health changes from Visit 1 (baseline) to Visit 2 (week 4) will be measured using a 5-point MGI scale (Lobene, 1986) and bleeding on probing will be measured using a 2 point scale, 'YES(1)' or 'NO (0)'. Changes from Visit 1 (baseline) to Visit 2 (week 4) in plaque scores will be measured using the O'Leary et al (1972) 2 point scale, 'YES(1)' or 'NO (0)'.

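### The primary plaque comparison names age and gender as example covariates but not baseline plaque, which is measured in everyone and would usually sharpen the estimate in arms of 10

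*Protocol*

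**What the plan says.** The Statistical Analyses section gives the model as a sentence fragment: "A mixed effects model with random effects for participants and fixed effect for treatment". It names no response variable, unit of analysis or visit term. The next sentence says that a 95% CI and the "mean difference (of change from baseline) in mean plaque levels at 4 weeks for each group will be reported".

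Covariates appear twice. The first statement is firm: "Adjustment for covariates (e.g. gender, age) will be included in the model". The second is conditional: "Where appropriate and data permitting covariates (e.g. age, gender) will be included in the model". Both lists are given by example, and neither includes baseline plaque.

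Baseline plaque is available. Under Study dental assessments, "Plaque scores will be recorded at Visit 1 and 2 following the method established by" a cited index, and "The same 2 teeth will be assessed by the clinician at Visit 1 and Visit 2 for plaque and gingival health". Each tooth has two plaque sites scored 0 or 1, so there are up to four binary values per participant per visit.

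Under Outcomes, Primary Objectives, "Changes from Visit 1 (baseline) to Visit 2 (week 4) in plaque scores will be measured". The Sample Size section also sizes the study on the difference in change. The objective in that Outcomes section is worded as a before-and-after evaluation, "prior and following the provision of a pictorial report and tailored OHI over a 4-week". The first Primary Objectives section, after Aims, asks for a comparison of the pictorial report with verbal instruction alone.

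**The concern.** With about 10 participants per arm, a chance difference in starting plaque is likely. Change depends on where a participant starts: the score is bounded, the inclusion criteria set no plaque threshold, and someone with no plaque at Visit 1 cannot improve. Subtracting baseline corrects for an imbalance only crudely, because it fixes the slope on baseline at 1. Regression on baseline estimates that slope. The study exists to estimate a difference with an interval, so unused information widens the one result it is meant to deliver.

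Two matters of wording add to this. A participant random effect is useful only with several rows per participant, and the protocol does not say what those rows are. Reporting by group, together with the before-and-after objective, leaves room for a within-arm result. Both arms receive oral hygiene instruction, so change within an arm does not isolate the effect of the report. For MGI, entry requires a score of at least 1 on at least one assessed tooth, so some fall is expected in both arms from regression to the mean.

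**Working it through.** **Inputs from the protocol.** 10 per arm, 20 in total, 1:1 allocation; the same two teeth at both visits; two binary plaque sites per tooth. Stated precision is within about 0.16 units, with an example of 0.69 (0.607 to 0.772). No SD and no baseline to week-4 correlation (rho) are given, so rho is an assumption, shown over 0.3 to 0.9.

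**The protocol's own figure.** Half-width = t × SD of change × sqrt(2/10), with t(0.975, 18 df) = 2.101. The example has full width 0.772 − 0.607 = 0.165 and half-width 0.0825. The implied SD of change is 0.0825 / (2.101 × 0.447) = 0.088. A half-width of 0.16 implies 0.170. The stated precision cannot be reproduced without an SD, and the two figures differ by a factor of two. That is a separate matter, so both are carried below.

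**Gain from baseline adjustment.** Let s be the SD at each visit, assumed equal.

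- Variance of change: 2(1 − rho)s².
- Residual variance given baseline: (1 − rho²)s².
- Ratio: (1 + rho)/2.

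Small-sample cost: multiply the variance by 1 + 1/16 for chance imbalance, and use t with 17 df (2.110) in place of 18 df (2.101). On the half-width this is sqrt(1.0625) × 2.110/2.101 = 1.035.

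| assumed rho | sqrt((1+rho)/2) | × 1.035 | CI narrower by | 0.0825 becomes | 0.16 becomes |
|---|---|---|---|---|---|
| 0.3 | 0.806 | 0.835 | about 16% | 0.069 | 0.134 |
| 0.5 | 0.866 | 0.896 | about 10% | 0.074 | 0.143 |
| 0.7 | 0.922 | 0.954 | about 5% | 0.079 | 0.153 |
| 0.9 | 0.975 | 1.009 | none | 0.083 | 0.161 |

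Break-even is where (1 + rho)/2 × 1.035² = 1, at rho of about 0.87.

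**Chance imbalance.** With equal variances, a baseline difference d between arms shifts the expected change-score difference by −(1 − rho)d. Take d as one standard error, s × sqrt(2/10), and divide the shift by the change-score half-width. The SD cancels and leaves sqrt((1 − rho)/2)/2.101. That is 0.28, 0.24 and 0.18 of the half-width at rho 0.3, 0.5 and 0.7. The change-score interval covers this shift on average over randomisations, but does not correct it in the trial actually run.

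**What the random effect does under each choice of rows.** Simulation used 400 trials of 10 per arm, with an assumed true difference in change of −0.30, SD 0.15 and rho 0.5.

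- One change score per participant: the treatment coefficient is the between-arm difference in change (mean −0.305). The random intercept cannot be separated from the residual.
- Site-level change with a participant random intercept: the target is recovered (−0.299) and the random effect is identifiable.
- Raw scores from both visits with treatment as the only fixed effect: the coefficient averages a baseline difference expected to be zero with the week-4 difference, giving half the target (−0.149).

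**The case against.** A reader might infer that the model cannot estimate the difference in change at all, or that the reported effect will be half the true one. The documents do not support this. The sentence after the model, the Sample Size section and the Outcomes section all make change from baseline the reported quantity. With change as the response, per participant or per site, treatment alone estimates the right difference and no visit term is needed. Halving arises only if both visits' raw scores are modelled with treatment alone, which runs against that text.

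It can also be said that comparing change scores is a legitimate choice, unbiased on average under randomisation; that the covariate list is open, so baseline plaque is not excluded; that a statistical analysis plan not shown here may name it; and that this is a 20-person pilot for estimation. All of that stands and limits the point to an improvement. It does not remove it: the protocol has already chosen a model and named example covariates, and an estimation study has most reason to use a baseline value it already holds.

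Nor can baseline plaque be called the best covariate on the evidence given. No correlation is stated, and the gain vanishes near 0.9.

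A within-arm headline result is improbable, since the Aims, the first Primary Objectives section, the parallel randomised design and the treatment effect all point to a between-arm contrast. The loose wording is worth tidying but would not carry the point alone.

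**Conclusion.** The concern holds as a matter of precision and handling of chance imbalance. The planned change-score comparison targets the right quantity, but leaves out a baseline measurement held on every participant. Adjusting for it would narrow the 95% CI by about 16%, 10% and 5% at rho of 0.3, 0.5 and 0.7, after paying for the extra coefficient, and by nothing near 0.9. These figures assume equal variances at the two visits, a linear relation with baseline, complete data on 20 participants and the stated values of rho. With at most four binary sites behind each score, the normal-theory figures are approximate. Omitting baseline does not bias the comparison on average.

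**What to change.** Make the primary analysis one row per participant: week-4 plaque proportion on treatment plus baseline plaque proportion, with no random effect. Report the adjusted between-arm mean difference with its 95% CI. Using change as the response gives the same treatment coefficient, because it only lowers the baseline slope by 1. Use the same form for mean MGI and percent bleeding, each with its own baseline.

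If several rows per participant are kept, use site-level change or week-4 rows with a participant random intercept, retaining baseline plaque as a covariate. Alternatively, model both visits with visit and treatment-by-visit terms. Do not fit treatment alone to both visits' scores. Keep the result on the mean-difference scale that the Sample Size and Statistical Analyses sections specify.

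Replace the two covariate statements with one definite list; each further coefficient takes another degree of freedom from 20 participants. Reword the by-group reporting and the before-and-after objective under Outcomes to match the between-arm comparison in the first Primary Objectives section.

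The cost is wording and one degree of freedom. No new data are needed.

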#### Secondary Objectives

- Patient perceptions of effectiveness of a having a pictorial report of their oral health as part of their dental care at Visit 1 and Visit 2
- Patient attitudes to oral health measured at Visit 1 and Visit 2
- Participants understanding of oral health vs oral disease at Visit 1 and Visit 2
- Assessment of the accuracy of the intra-oral camera's ability to assess plaque levels compared to the clinician using traditional techniques using dye

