#### **Expected outcomes**

It would be expected from this pilot study that the provision of a pictorial report of the participants oral health with tailored oral health instruction used as a "tailored" patient education tool demonstrating effective oral hygiene techniques, would improve participants' oral health. The improvement will be demonstrated with decreased plaque and MGI scores. It is also expected that the intra-oral camera will have a similar accuracy in measuring participants plaque scores compared to traditional method using dye to highlight plaque.

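### The analysis rule for secondary outcomes gives camera accuracy a treatment-effect model, and the protocol does not tie the camera reading to the two teeth scored with dye

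*Protocol*

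**What the plan says.** The Protocol lists, under Secondary Objectives and again under Outcomes, "Assessment of the accuracy of the intra-oral camera's ability to assess plaque levels compared to the clinician using traditional techniques using dye". Expected outcomes adds the expectation that "the intra-oral camera will have a similar accuracy in measuring participants plaque scores compared to traditional method using dye".

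Statistical Analyses describes the primary analysis as "A mixed effects model with random effects for participants and fixed effect for treatment", reported as a between-group difference in change in plaque. It then sets one rule for everything else: "For each secondary outcome, similar analyses will be performed as the primary outcome using a generalized linear model with an appropriate link function". The sentence goes on to let the link depend on the type of outcome. It makes no exception for camera accuracy.

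Study dental assessments defines the two measurements. Of the camera's plaque function it says "This function will be used to assess the plaque levels present on the upper 3-3", before any dye is applied. For the clinician's scoring, "The teeth for gingival health and plaque assessment within the study will be 2 suitable teeth within the upper 3-3 region", and "The same 2 teeth will be assessed by the clinician at Visit 1 and Visit 2 for plaque and gingival health". The dye score is binary on two surfaces per tooth. The section gives neither the scale nor the unit (tooth, surface or region) of the camera reading.

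**The concern.** Accuracy against a reference is a paired question: at a given site, does the camera say what the dye says? A model with treatment as its fixed effect asks whether the arms differ. Changing the link function adapts that model to a binary, ordinal or continuous outcome; it does not turn an arm contrast into a measure of agreement. An analysis that follows the sentence could therefore appear to support the expectation about the camera without testing it.

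The second part concerns the units compared. If the camera yields one plaque level for the region and the dye yields a score on two teeth, differences between them mix camera error with ordinary variation between teeth. Unless the camera reading is captured by tooth when it is made, the matching may not be recoverable later.

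At stake is one stated secondary objective. The primary comparison of the arms is not affected.

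**Working it through.** The Protocol gives no figure for camera-versus-dye agreement, so there is none to reproduce. The checks below are illustrations; prevalence, intraclass correlation (ICC) and kappa are assumptions.

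**Inputs from the Protocol.** 20 participants, 10 per arm (Sample Size); 2 dye teeth with 2 binary surfaces each, so 4 dye sites per participant per visit (Study dental assessments); at least 4 teeth in the upper anterior sextant (Inclusion Criteria), so the camera region holds 4 to 6 teeth, or 8 to 12 surfaces; two visits.

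**1. Can an arm contrast detect poor agreement?** Assume plaque on 60% of sites in one arm and 40% in the other, with independent sites.
- Both cameras have expected arm difference 0.60 − 0.40 = 0.20. Its SD is √(2 × 0.24/40) = 0.11, with 40 sites per arm.
- Camera identical to dye: kappa = 1.
- Camera independent of dye within arm: observed agreement = 0.6² + 0.4² = 0.52 in each arm. The pooled marginals are 0.5, so chance agreement = 0.50 and kappa = (0.52 − 0.50)/(1 − 0.50) = 0.04.
- Simulation (4,000 runs) gave the same: differences 0.202 and 0.201, SD 0.110 for both, mean kappa 1.000 and 0.039.

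**2. Do similar mean scores help?** Assume dye shows plaque on 70% of sites and a camera flags 70% at random. The means are equal, sensitivity is 0.70 and specificity 0.30. Observed agreement = 0.49 + 0.09 = 0.58, which equals chance agreement, so kappa = 0.

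**3. What does the tooth mismatch do on its own?** Take a camera that is right at every site, average it over m surfaces, and subtract the dye score on 4 of those surfaces:

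Var(difference) = p(1 − p)(1 − ICC)(1/4 − 1/m); limits of agreement = ±1.96 × SD.

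| Camera teeth | m | p = 0.5, ICC = 0.1 | p = 0.7, ICC = 0.5 |
|---|---|---|---|
| 6 | 12 | 0.25 × 0.9 × 1/6 = 0.0375; ±0.38 | 0.21 × 0.5 × 1/6 = 0.0175; ±0.26 |
| 4 | 8 | 0.25 × 0.9 × 1/8 = 0.0281; ±0.33 | 0.21 × 0.5 × 1/8 = 0.0131; ±0.22 |

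With 6 teeth, the simulated correlation between the two scores was 0.73 to 0.93, and the scores coincided exactly in 17% to 49% of participants. None of this is camera error. The share of camera teeth without a dye reference is 2/4 to 4/6, that is, half to two thirds.

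**4. What would a matched comparison offer?** Paired sites: 2 teeth × 2 surfaces × 20 = 80 per visit, 160 over both visits, if data are complete. For an assumed kappa of 0.70 at 50% prevalence (observed agreement 0.85, chance 0.50), the 95% half-width is 1.96 × √(0.85 × 0.15/n)/0.50:
- ignoring clustering: 0.16 (n = 80) or 0.11 (n = 160);
- with a design effect of 1.9, which is 1 + 3 × 0.3 for 4 sites at ICC 0.3: 0.22 or 0.15;
- if all 8 sites over both visits share that ICC, the design effect is 1 + 7 × 0.3 = 3.1, and the half-width for 160 sites is 0.111 × √3.1 = 0.19.

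**The case against.** The analysis sentence is a generic rule for four dissimilar items. It asks for similar, not identical, analyses and lets the form depend on the outcome. It never says that camera accuracy will be tested as an arm difference, and a statistical analysis plan, not shown, may name an agreement analysis. Part of this stands: a missing agreement statistic is not itself a fault, because that choice is commonly left to the analysis plan. What does not fall away is that the Protocol fixes a rule for every secondary outcome, that camera accuracy is one of them, and that the latitude given concerns the link and not the question asked.

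Three stronger readings are tempting, and the documents do not support them.
- *Camera and dye are scored on different teeth.* They are not: the 2 dye teeth lie inside the camera region, so the sets are nested. The extra camera teeth do harm only if the whole region is compared with the 2 teeth, and the Protocol neither says nor rules out that this will happen.
- *The trial's data cannot show agreement.* They could, if the camera output is kept by tooth and surface. The limitation belongs to the treatment-effect model and to unmatched scores.
- *Dye is read with knowledge of the camera result, so agreement is inflated.* Study Design implies that one clinician does both the scans and the dental assessments, and the camera reading precedes dye. But no section says that this clinician sees a camera plaque score before scoring the dye. Upward bias is a possible risk, not a demonstrated one.

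It is also fair that site-level statistics need a per-surface camera reading, which the Protocol does not define.

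**Conclusion.** The point holds in this form. As worded, the rule assigns camera accuracy to a model that estimates an arm difference and would not answer the objective: the same 0.20 arm difference is compatible with kappa of 1.00 or 0.04. The Protocol also leaves open a comparison of whole-region camera scores with two-tooth dye scores, in which a perfect camera would show limits of about ±0.22 to ±0.38.

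The first conclusion rests on the wording and does not depend on the assumed prevalences, which only illustrate it. The size of the second depends on the assumed prevalence (0.5 to 0.7), the assumed ICC (0.1 to 0.5) and the number of teeth present. It arises only if the comparison is not restricted to the shared teeth. The change should be made, since a stated objective would otherwise go unanswered.

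**What to change.** - Exempt camera accuracy from the sentence on secondary outcomes in Statistical Analyses.
- In Study dental assessments, state that the camera plaque reading is recorded by tooth and surface for the same 2 teeth scored with dye, at both visits.
- Report paired agreement with dye as the reference: sensitivity, specificity and kappa, with confidence intervals that allow for clustering within participant. State the maximum of 80 paired sites per visit (160 in all).
- If the camera output cannot be read by surface, make the paired comparison at the finest level available on those 2 teeth, and say so.
- As a precaution, take the camera reading from the stored pre-dye images without sight of the dye scores. Merely fixing the camera score before dye is applied would not mask the person who then reads the dye.

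The cost is a wording change and a short case report form instruction. No extra participants or visits are needed. Intervals will be wide with 20 participants, and the result should be presented as an estimate of agreement, not as proof of equivalence.
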